7 STATISTICAL ANALYSES

7.1 General Methods

Unless otherwise noted, the bulleted titles in the following subsections describe tabulations of discrete variables, by the frequency and proportion of participants falling into each category, grouped by treatment (with total). Percentages given in these tables will be rounded and, therefore, may not always sum to 100%. Continuous variables will be summarized by cohort (with total) using the mean, standard deviation, median, minimum and maximum values.

Time to event distribution (e.g., progression free survival, overall survival and duration of response) will be estimated using Kaplan Meier techniques. Median survival time along with 95% CI will be constructed based on a log-log transformed CI for the survivor function $S(t)$ ^{5,6}. Rates at fixed time points (e.g., PFS at 6 months) will be derived from the Kaplan Meier estimate and corresponding confidence interval will be derived based on Greenwood formula for variance derivation and on log-log transformation applied on the survivor function $S(t)$ ⁷.

Confidence intervals for binomial proportions will be derived using the Clopper-Pearson method¹. All analyses will be performed separately for each cohort upon completion of follow-up for the primary endpoint in each cohort. There will be no multiplicity adjustment for p-values.

7.2 Study Conduct

7.2.1 Accrual

The following will be summarized on the enrolled population:

- Number of participants accrued by country and investigational site
- Number of participants accrued by month

A by participant listing of accrual will be produced.

7.2.2 Relevant Protocol Deviations

The following programmable deviations will be considered as relevant protocol deviations. Non-programmable relevant eligibility and on-treatment protocol deviations, as well as significant (both programmable and non-programmable) eligibility and on-treatment protocol deviations will be reported through ClinSIGHT listings.

At entrance:

- Participants without measurable disease at baseline
- Participant with baseline Karnofsky performance status < 70
- Participants with pathologically confirmed PCNSL or PTL who didn't meet the eligibility criteria of progressing after or not responding to at least 1 line of systemic therapy
- For subjects enrolled afterprotocol amendment 9, patients had more than 2mg/day dexamethasone equivalent in the 14 days prior to the first nivolumab dose

On-Study:

- Participants receiving concurrent anti-cancer therapy (systemic, surgery, non-palliative radiotherapy, transplant) other than nivolumab.

A summary table and a by participant listing of relevant protocol will be produced.

7.3 Study Population

7.3.1 Subject Disposition

The total number of participants enrolled (treated or not) will be presented along with the reason for not being treated.

Number of participants who discontinued treatment along with corresponding reason will also be tabulated.

7.3.2 Demographics and Other Baseline Characteristics

Descriptive statistics will be summarized the following baseline characteristics for all treated participants. All baseline presentations will identify participants with missing measurements.

- Age (descriptive statistics)

- Age categories (< 30, ≥ 30 and < 45, ≥ 45 and < 60, ≥ 60)
- Gender (male, female)
- Race (white, black or african american, asian, american indian or alaska native, native hawaiian or other pacific islander, other)
- Baseline Karnofsky Performance Status (median and range, ≥ 90, ≥ 70 and < 90, < 70)
- Weight (descriptive statistics)
- Time from initial disease diagnosis to first dose of study medication (median, range, < 3 months; ≥ 3 months)
- Region (US/Canada, Europe, Rest of the World)
- Smoking Status (Yes, No, Unknown)
- Disease stage at initial diagnosis (PTL cohort only) (stage 1 or 2, 3, 4, unknown)
- Disease status at study entry (relapsed, refractory, or relapsed and refractory)
- CNS involvement at study entry (PTL cohort only) (Yes, No, unknown)
- Ocular involvement (Yes, No, unknown)
- All lesions (Investigator Tumor Assessments at Baseline): sites of diseases, number of disease sites per participant
- Target Lesions (Investigator Tumor Assessments at Baseline): Presence of target lesions, site of target lesion, sum of product diameters of target lesions.

The same analysis would be performed by subjects enrolled pre- vs. post-amendment 9 for PCNSL cohort as well as by subjects high dose versus low dose of corticosteroids at baseline.

7.3.3 *Medical history- Concurrent diseases*

General medical history will be listed by participant and pretreatment events will be tabulated.

7.3.4 *Prior therapy agents*

For participants with PCNSL, prior therapy includes high-dose methotrexate (HD-MTX), HD-MTX-based regimen, high-dose cytarabine, radiation therapy alone as treatment or as part of consolidation therapy, high-dose therapy with autologous stem cell transplant as part of consolidation therapy, and/or intraocular MTX alone or as part of consolidation therapy.

For participants with PTL, prior therapy includes chemo-immunotherapy (e.g., CHOP-R or any other regimens), with/without prophylactic RT to contralateral testis or orchiectomy or intrathecal chemotherapy.

The following will be summarized for PCNSL and PTL (as appropriate):

- Number of participants who received Prior Systemic Cancer Therapy by type (such as but may not be limited to Immunotherapy by Monoclonal Antibodies, Steroid, Chemotherapy – Other than anthracyclines, Chemotherapy - Anthracyclines, Kinase Inhibitors, Immunomodulatory Derivatives, Radioimmunotherapy, Other)
- Number of participants by type of regimen for first and second lines of therapy

- Number of lines of prior systemic therapies received (median, range, 1, 2, 3, 4, ≥ 5)
- Time from completion of most recent prior regimen to treatment (median, range, < 3, 3 - 6, > 6 months)
- Prior radiotherapy (yes or no, not reported)
- Prior orchiectomy (yes or no, not reported)
- Prior autologous transplant (Yes, No, Not reported)
- Prior allogeneic transplant (Yes, no, Not reported)
- Prior surgery related to cancer (Yes, No, Not reported)

Other Prior therapy:

- Prior/current non-study medication classified by anatomic and therapeutic classes.

Medication will be reported using the generic name. A listing by participant will also be provided.

7.3.5 *Baseline examinations*

Participants with abnormal baseline physical examination will be tabulated by examination criteria and by cohort.

7.4 *Extent of Exposure*

Analyses in this section will be performed in all treated participants.

7.4.1 *Administration of study therapy*

The following parameters will be summarized (descriptive statistics):

- Relative dose intensity (%) using the following categories: < 50%; 50 - < 70%; 70 - < 90%; 90 - < 110%; $\geq 110\%$.
- Number of doses received (summary statistics)
- Cumulative dose
- Duration of treatment: duration of treatment will be presented using a Kaplan-Meier curve whereby the last dose date will be the event date for participants who discontinued study therapy. Participants who are still on study therapy will be censored on their last dose date. Median duration of treatment and associated 95% CI will be provided.
- A by-participant listing of dosing of study medication (record of study medication, infusion details, dose change) and a listing of batch number will be also provided.

Table 7.4.1-1: *Administration of study therapy: definition of parameters*

nivolumab	
Dosing schedule per protocol	240mg Q2W for first 8 cycles; 480 Q4W starting cycle 9
Dose	Dose mg is defined as Total Dose administered (mg). Dose administered in mg at each dosing.

Table 7.4.1-1: Administration of study therapy: definition of parameters

nivolumab	
Cumulative Dose	Cum dose (mg) is sum of the doses (mg) administered to a participant during the treatment period.
Cumulative Planned Dose	For subjects who only receive 240mg Q2W up to cycles 8, cumulative planned dose in cycles 1-8 is (min(Last dose date within cycles 1-8 + 14 day, death date) - Start dose date) x 480mg / 28 day For subjects receive 480 Q4W starting cycle 9, cumulative planned dose from cycle 9 is (min(Last dose date + 28 day, death date) - Start dose date of cycle 9) x 480mg / 28 day
Relative dose intensity (%)	Cum dose /Cumulative Planned Dose x 100
Duration of treatment	Last dose date - Start dose date +1

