4.5 Selection and Timing of Dose for Each Subject

4.5.1 Nivolumab Dose and Schedule

Subjects should receive nivolumab at a dose of 240 mg as a 30-minute infusion on Day 1 of each treatment cycle for the first 8 cycles until progression, unacceptable toxicity, withdrawal of consent, or the study ends, whichever occurs first. Subjects should begin study treatment within 3 calendar days of treatment assignment. Beginning with Cycle 9, subjects should receive nivolumab at a dose of 480 mg as a 30-minute infusion until progression, unacceptable toxicity, withdrawal of consent, or the study ends, whichever occurs first.

There will be no dose escalations or reductions of nivolumab allowed. Subjects may be dosed no less than 12 days from the previous dose. For Q4W dosing cycles, subjects may be dosed within a +/- 3-day window. Premedications are not recommended for the first dose of nivolumab.

Subjects should be carefully monitored for infusion reactions during nivolumab administration. If an acute infusion reaction is noted, subjects should be managed according to [Section 4.5.8](#).

Doses of nivolumab may be interrupted, delayed, or discontinued depending on how well the subject tolerates the treatment. Dosing visits are not skipped, only delayed.

Information regarding infusion details for nivolumab can be found in the Investigator Brochure.⁶⁴

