7.4.2.4 Dose Reductions/Escalation

There will be no dose escalations or reductions of nivolumab allowed.

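### The planned-dose formula stops at the death date although the last dose was given in full, so death within 14 days of a Q2W dose inflates relative dose intensity

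*SAP*

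**What the plan says.** The definitions are in SAP Section 7.4.1, Table 7.4.1-1.

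- **Schedule:** "240mg Q2W for first 8 cycles; 480 Q4W starting cycle 9".
- **Numerator:** "Cum dose (mg) is sum of the doses (mg) administered to a participant during the treatment period". Nothing is prorated.
- **Planned dose, participants treated only in Cycles 1-8:** "min(Last dose date within cycles 1-8 + 14 day, death date) - Start dose date) x 480mg / 28 day".
- **Planned dose, Cycle 9 onward:** "min(Last dose date + 28 day, death date) - Start dose date of cycle 9) x 480mg / 28 day".
- **RDI:** "Cum dose /Cumulative Planned Dose x 100".

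The same section lists "Relative dose intensity (%) using the following categories", and the top category is 110% or more. Exposure is analysed in all treated participants, so anyone with a single dose is included. SAP Section 7.4.2.4 adds: "There will be no dose escalations or reductions of nivolumab allowed".

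Protocol Section 4.5.1 fixes when the dose falls within the cycle: "Subjects should receive nivolumab at a dose of 240 mg as a 30-minute infusion on Day 1 of each treatment cycle for the first 8" (the 8 being the Q2W cycles). It also sets a minimum of 12 days between doses. Protocol Table 5.1-2 gives a window of 2 days either side for Q2W dosing.

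**The concern.** RDI should compare what was delivered with what was planned over the same period. Here the two sides follow different rules. The numerator credits the last dose in full. The denominator credits only the part of the last interval that the participant lived through. Two participants with identical dosing can therefore receive very different values solely because one of them died.

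The exposure table is at stake. A participant who died shortly after a dose given on schedule can appear in the top RDI category, which would normally be read as more drug than planned, in a trial that allows no escalation. Cohorts of 45 and 20 are small enough for one such participant to be visible: 1/45 = 2.2% and 1/20 = 5% of the cohort.

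**Working it through.** The documents state no RDI value to reproduce, so the check evaluates the table's formulas directly.

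**Inputs.** Dose 240 mg every 14 days (SAP Table 7.4.1-1), whole dose on Day 1 (Protocol 4.5.1), planned rate 480/28 = 240/14 = 17.143 mg per day.

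**Formula.** Take n doses exactly 14 days apart and death d days after the last, with d at most 14.

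- Dose given = 240n.
- Planned dose = (14(n-1) + d) × 480/28.
- RDI = 14n/(14(n-1) + d).

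**Baseline check.** With survival of at least 14 days after the last dose, d is replaced by 14 and RDI = 14n/14n = 100% for every n from 1 to 8. The formula is right for survivors.

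**With death inside the last interval:**

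| n | d = 1 | d = 3 | d = 7 | d = 10 | Last day d with RDI of 110% or more |
|---|---|---|---|---|---|
| 1 | 1400% | 467% | 200% | 140% | 12 |
| 2 | 187% | 165% | 133% | 117% | 11 |
| 3 | 145% | 136% | 120% | 111% | 10 |
| 4 | 130% | 124% | 114% | 108% | 8 |
| 8 | 113% | 111% | 107% | 104% | 3 |

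The last column solves d ≤ 14n/1.1 - 14(n-1). For n = 1 the limit is 12.7, and for n = 8 it is 101.8 - 98 = 3.8.

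As a worked case, one dose and death 3 days later gives a planned dose of 3 × 17.143 = 51.4 mg, and 240/51.4 = 467%. For n = 1 and d = 0 the planned dose is zero and RDI is undefined.

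**What permitted dosing can produce without a death.** At the 12-day minimum throughout, a survivor scores 14n/(12(n-1) + 14):

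- n = 3: 42/38 = 110.5%
- n = 4: 56/50 = 112%
- n = 8: 112/98 = 114.3%

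The ratio cannot exceed 14/12 = 117%.

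**Cycle 9 onward.** The same cap applies over 28 days. For one 480 mg dose after eight on-schedule Q2W doses, with death one day later:

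- If numerator and denominator both cover only Cycle 9 onward: 480/17.143 = 2800%.
- If the Cycle 1-8 planned dose is added: (1920 + 480)/(1920 + 17.14) = 123.9%.

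The table does not say how the two planned-dose terms combine, so the effect here cannot be sized more closely.

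**Effect on a mean, if one is reported.** In a cohort of 20, one value of 466.7% with nineteen at 100% gives (466.7 + 1900)/20 = 118%.

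**The case against.** One defence is that the cap avoids charging participants for doses they did not live to receive. It does not hold. The window already ends one interval after the last dose actually given, and the dose for that interval was delivered on its first day. Removing the death date charges for no undelivered dose.

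Other objections limit the point, and they stand.

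- **The top category has legitimate occupants.** A reader might infer from the ban on escalation that nobody dosed within the rules can reach 110%. The permitted 12-day interval contradicts that: living participants can score 110.5% to 114.3%.
- **No count is available.** A reader might infer that the top category would fill with early deaths. The documents give no rate of death within one to two weeks of a dose, and entry requires a Karnofsky status of 70 or more. The relevant event is death within a short window after the last dose, not early death in general.
- **1400% is the single worst finite value in Cycles 1-8.** It needs death exactly one day after the only dose. By the fourth dose, death at 7 days gives 114%.
- **Categories blunt the extremes.** A participant at 1400% counts the same as one at 110%. Extreme values matter only if a mean or maximum is also shown, which the reference to descriptive statistics permits but does not clearly require. Number of doses, cumulative dose and a dosing listing are also reported, so a careful reader could see that a participant had only one dose.

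**Conclusion.** The formula is wrong as written, and no other section corrects it. Death within 14 days of the last Q2W dose raises RDI although dosing was as planned. At exact 14-day spacing, participants land in the top category if death comes within 12, 11, 10, 8 or 3 days of the last dose for n = 1, 2, 3, 4 or 8. Values above about 117% in Cycles 1-8 cannot come from permitted dosing and would be products of the formula. Values from 110% to 114.3% could have either cause.

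The consequence is small. The number of participants affected is unknown and could be none to a few of the planned 45 and 20. RDI is a descriptive exposure measure: ORR, DOR, PFS and OS do not use it, and no decision rule in the documents depends on it. The figures assume exact 14-day spacing and a literal reading of the table. The size of the effect from Cycle 9 onward stays open until the table states how its two planned-dose terms combine.

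**What to change.** Delete the death date from both planned-dose terms in Table 7.4.1-1:

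- Cycles 1-8: (last dose date within Cycles 1-8 + 14 - start date) × 240/14.
- Cycle 9 onward: (last dose date + 28 - Cycle 9 start date) × 480/28.

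A participant dosed at exact 14-day intervals in Cycles 1-8 then scores 100% whenever death occurs. For one dose and death a day later, the planned dose is 14 × 240/14 = 240 mg and RDI is 240/240 = 100%. The zero denominator also disappears. Participants dosed at shorter permitted intervals will still score somewhat above 100%, as they should.

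The same edit should state how the two terms are combined for participants who pass Cycle 8.

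The cost is a small edit to one SAP table and its derivation program. Treatment, data collection and the efficacy analyses are unchanged.

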7.4.2 Modifications of Study Therapy**7.4.2.1 Dose delays****7.4.2.2 Dose delays**

Treatment may be delayed for up to a maximum of 6 weeks from the last dose. A dose will be considered as actually delayed if the delay is exceeding 3 days (i.e., greater than or equal to 4 days from scheduled dosing date). Length of delay is defined as (duration of previous cycle in days - 14). Dose delays will be divided into following categories: 4 - < 8 days, 8 - < 15 days, 15 - < 43, ≥ 43 days. Reason for dose delay will be retrieved from CRF dosing pages.

The following parameters will be summarized:

- Number of participants with at least one dose delayed, number of dose delayed per participant, Length of Delay and Reason for Dose Delay

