- Any event that leads to delay in dosing lasting $>$ 6 weeks from the previous dose requires discontinuation, with the following exceptions:
 - Dosing delays to allow for prolonged steroid tapers to manage drug-related AEs are allowed. Prior to re-initiating treatment in a subject with a dosing delay lasting $>$ 6 weeks from the previous dose, the BMS Medical Monitor must be consulted. Tumor assessments should continue as per protocol even if dosing is delayed. Periodic study visits to assess safety and laboratory studies should also continue every 6 weeks or more frequently if clinically indicated during such dosing delays.
 - Dosing delays lasting $>$ 6 weeks from the previous dose that occur for non-drug-related reasons may be allowed if approved by the BMS Medical Monitor. Prior to re-initiating treatment in a subject with a dosing delay lasting $>$ 6 weeks, the BMS Medical Monitor must be consulted. Tumor assessments should continue as per protocol even if dosing is delayed. Periodic study visits to assess safety and laboratory studies should also continue every 6 weeks or more frequently if clinically indicated during such dosing delays.
- Any AE, laboratory abnormality, or intercurrent illness which, in the judgment of the investigator, presents a substantial clinical risk to the subject with continued nivolumab dosing

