Targeted Physical Examination	X	X	Include assessment of lymph node areas (eg, submandibular, cervical, supraclavicular, axillary, or inguinal lymph node), abdominal organs (eg, spleen) and neurological examination
Vital Signs	X	X	Temperature, BP, HR
Adverse Events Assessment	-----Continuously-----		Assessed using NCI CTCAE v. 4.03
Review of Concomitant Medications	X	X	
Physical Measurements	X	X	Includes weight
Karnofsky Status	X	X	
Laboratory Tests		X	To be done within 72 hours prior to dosing and include: CBC with differential, uric acid, BUN or serum urea level, creatinine, Ca, Mg, K, Cl, Na, amylase, lipase, glucose, phosphate, AST, ALT, TBIL, ALP, albumin, LDH. Cycle 1 Day 1: Laboratory tests do not need to be repeated if performed within 14 days prior to first dose.
Thyroid Function Testing		See Note	Thyroid function testing (TSH with reflexive fT3 and fT4) is to be done every 6 weeks (every 3 infusions) for subjects receiving nivolumab at 240 mg Q2W, then every 8 weeks for subjects receiving nivolumab at 480 mg qw4 (every other infusion)
Pregnancy Test (WOCBP only)	X	See Note	Serum or urine within 24 hours prior to first dose and then at least once every 4 weeks (\pm 1 week) regardless of dosing schedule.

Table 5.1-2: On Treatment Procedures (CA209647)

Procedure	Cycle 1 Day 1	Cycle 2 & Beyond, Day 1	Notes
			All windows proposed are calendar days. Procedures must be done within 72h prior to dosing unless otherwise specified. Cycle duration is 2 weeks until 8 doses have been completed; subsequent cycles are 4 weeks in duration.

Table 5.1-2: On Treatment Procedures (CA209647)

Procedure	Cycle 1 Day 1	Cycle 2 & Beyond, Day 1	Notes
			
All windows proposed are calendar days. Procedures must be done within 72h prior to dosing unless otherwise specified. Cycle duration is 2 weeks until 8 doses have been completed; subsequent cycles are 4 weeks in duration.

Outcomes Research Questionnaire			
EQ-5D 3L (PCNSL and PTL cohorts) EORTC QLQ C30 (PCNSL and PTL cohorts) EORTC QLQ-BN20 (PCNSL only)	X	X	Subjects will be asked to complete the questionnaires prior to dosing Day 1 Week 1 and then prior to each radiographic tumor assessment. Refer to Section 5.6.6 for more information.

Table 5.1-2: On Treatment Procedures (CA209647)

Procedure	Cycle 1 Day 1	Cycle 2 & Beyond, Day 1	Notes
PK and Immunogenicity Assessments			
PK and Immunogenicity Samples			See Table 5.5-1 for sampling details.

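### The SAP's length-of-delay formula subtracts 14 days from every cycle, so from the Cycle 10 dose on each 4-weekly delay is reported 14 days too long and usually in the wrong category

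*SAP*

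**What the plan says.** SAP Section 7.4.2.2 sets out four things about dose delays.

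- **Limit:** "Treatment may be delayed for up to a maximum of 6 weeks from the last dose".
- **Flag:** a dose counts as delayed when it is "greater than or equal to 4 days from scheduled dosing date".
- **Length:** "Length of delay is defined as (duration of previous cycle in days - 14" days), with no separate rule for the 4-weekly part of treatment.
- **Categories:** "Dose delays will be divided into following categories: 4 - < 8 days, 8 - < 15 days, 15 - < 43", and then 43 days or more.

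The number of participants with a delay, the number of delayed doses, the length of delay and the reason are all to be summarized.

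On the schedule, Protocol Table 5.1-2 says: "Cycle duration is 2 weeks until 8 doses have been completed; subsequent cycles are 4 weeks in duration". SAP Table 7.4.1-1 agrees: "240mg Q2W for first 8 cycles; 480 Q4W starting cycle 9". The same SAP table uses a 28-day interval from Cycle 9 when it computes the cumulative planned dose.

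Protocol Section 4.5.5 allows exceptions to the 6-week limit. One reads: "Dosing delays to allow for prolonged steroid tapers to manage drug-related AEs are allowed". Another covers delays for reasons unrelated to the drug, with Medical Monitor approval.

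SAP Section 7.4.1 also reports "Relative dose intensity (%) using the following categories: < 50%; 50 - < 70%; 70 - < 90%; 90 - < 110"% and a top category of 110% or more. Table 7.4.1-1 gives one planned-dose expression for participants who receive only the 2-weekly schedule and another counted from the start of Cycle 9. It does not say that the two are added for a participant who receives both.

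**The concern.** A delay is the actual interval minus the planned interval. The SAP fixes the planned interval at 14 days although its own exposure table and the protocol double it from Cycle 9. A 4-weekly dose given exactly on schedule therefore has a computed length of 14 days, and a dose 4 days late has 18.

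Length of delay is a reported parameter with fixed categories. If the rule is programmed as written, minor slips late in treatment appear in the study report as delays of more than two weeks. For flagged doses from Cycle 10 on, the two lowest categories cannot be filled at all. Treatment can last two years and the error starts at week 20, so it covers most of the planned schedule for anyone who stays on treatment.

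The planned-dose definition raises a second, smaller problem of the same kind at the change from 2-weekly to 4-weekly dosing.

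**Working it through.** **Inputs.** Planned cycle length is 14 days for Cycles 1 to 8 and 28 days from Cycle 9 (Protocol Table 5.1-2; SAP Table 7.4.1-1). The subtracted constant is 14, the flag is 4 days or more after the scheduled date, and the limit is 42 days from the last dose (SAP 7.4.2.2). In whole days the categories are 4–7, 8–14, 15–42 and 43 or more.

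**Where the SAP's 14 is right.** For a dose that is d days late:

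SAP length = (planned length of the previous cycle + d) − 14

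- Doses of Cycles 2 to 9: the previous cycle is one of Cycles 1 to 8, so length = 14 + d − 14 = d. This is correct, and it includes the Cycle 9 dose because Cycle 8 is a 14-day cycle.
- Doses from Cycle 10 on: length = 28 + d − 14 = d + 14. This is 14 days too long.

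The Cycle 10 dose is due 8 × 14 + 28 = 140 days after the first dose.

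**Effect on the categories for 4-weekly doses**

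| Days since previous dose | True delay | SAP length | Correct category | SAP category |
|---|---|---|---|---|
| 32–35 | 4–7 | 18–21 | 4–7 | 15–42 |
| 36–42 | 8–14 | 22–28 | 8–14 | 15–42 |
| 43–56 | 15–28 | 29–42 | 15–42 | 15–42 |
| 57–70 | 29–42 | 43–56 | 15–42 | 43 or more |
| 71 or more | 43 or more | 57 or more | 43 or more | 43 or more |

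Within the 6-week limit only the first two rows can occur (42 − 28 = 14 days late at most), and all 11 whole-day intervals in them are misclassified. The lower three rows need one of the exceptions in Protocol Section 4.5.5.

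**Effect on the mean.** If a share f of all delayed doses falls at Cycle 10 or later, the mean length is inflated by 14 × f days. The documents do not give f. Assuming 10%, 25% or 50%, the inflation is 1.4, 3.5 or 7 days.

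**Planned dose and relative dose intensity (RDI).** Take a participant with 8 doses of 240 mg (1920 mg) and k doses of 480 mg, all on time except that Cycle 9 starts L days late.

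- *Terms added.* Planned dose = (112 + 28k) × 480/28 = 1920 + 480k mg, which equals the dose given, so RDI is shown as 100% whatever L is. The L days fall in neither term. Counting them gives RDI = (112 + 28k)/(112 + 28k + L).
- *At L = 28* (42 days after Cycle 8, the 6-week limit): k = 1 gives 140/168 = 83.3%; k = 2, 168/196 = 85.7%; k = 3, 196/224 = 87.5%; k = 4, 224/252 = 88.9%; k = 5, 252/280 = 90.0%.
- *When the category changes.* RDI falls below 90% once L exceeds (112 + 28k)/9. That is from 16 days late for k = 1, 19 for k = 2, 22 for k = 3 and 25 for k = 4, in each case up to the 28-day limit. For k = 5 it would need 29 days, which is beyond the limit.
- *Terms not added.* If a participant who reaches Cycle 9 gets only the second term, on-time RDI is (1920 + 480k)/(480k). That is 2400/480 = 500% at k = 1. At k = 22, which fills the 88 weeks left of two years after week 16, it is 12480/10560 = 118%. Every such participant would fall in the 110%-or-more category.

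**The case against.** The best argument against giving this much weight is that nothing inferential depends on it. Length of delay and RDI are descriptive, no decision rule uses them, only participants still being dosed at week 20 or later contribute, and a by-participant dosing listing is planned from which true intervals should be recoverable. All of that is correct and limits the importance of the point. It does not make the tables right.

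A second objection is that the count of delayed doses may not be safe either. The SAP explains the flag by the scheduled date, so the counts are correct on the natural reading. The next sentence, however, defines length as duration minus 14. A programmer who built the flag from that length would mark every on-time 4-weekly dose as delayed, because intervals of 25 to 31 days (the ±3-day window in Protocol Section 4.5.1) score 11 to 17. This is a risk of misprogramming and not what the text says. The same correction removes it.

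A third objection is that the 83.3% to 90.0% RDI figures assume the two planned-dose terms are added, which the SAP does not state. That is fair: those figures are conditional on the sum, on all other doses being on time and on Cycle 9 being as late as the limit allows. The literal alternative gives a worse result (118% to 500% for on-time dosing), so the need for one explicit formula stands on either reading.

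**Conclusion.** The length-of-delay formula is wrong as written for every dose from Cycle 10 on. The excess is exactly 14 days, and it rests on no assumption beyond the planned cycle lengths, which both documents state. Within the 6-week limit every flagged 4-weekly delay is put in the wrong category; beyond it, true delays of 29 to 42 days also move up one category. The size of the effect on the summary statistics depends on the unknown share of delayed doses at Cycle 10 or later.

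With the flag tied to the scheduled date, the counts of delayed doses and of affected participants are correct. The planned-dose definition is incomplete for participants who reach Cycle 9. If its terms are summed, a late Cycle 9 within the limit puts RDI in the wrong category only when four or fewer 4-weekly doses follow, given that all other doses are on time.

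Efficacy results are untouched. This should be corrected because the error in the reported tables is certain and costs almost nothing to remove.

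**What to change.** In SAP Section 7.4.2.2, define length of delay as the duration of the previous cycle in days minus the planned length of that cycle, with planned length 14 days for Cycles 1 to 8 and 28 days from Cycle 9. The length then agrees with the existing flag for every dose.

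In SAP Table 7.4.1-1, give one cumulative planned dose for participants who reach Cycle 9: (min(last dose date + 28 days, death date) − first dose date) × 480 mg / 28 days. Because 240 mg per 14 days and 480 mg per 28 days are the same daily rate, this one expression covers both phases, closes the gap before a late Cycle 9 and leaves the death-date convention as it is. Check at k = 1, L = 28: planned 168 × 480/28 = 2880 mg, given 2400 mg, RDI 83.3%.

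The cost is two lines of SAP text and the matching derivations. No new data are needed, and no dosing rule changes.
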